11.3.1.2. Presence of Severe RSV-LRTI as Assessed by the Clinical Endpoint Committee (CEC)

For subjects with an RTI that is considered severe by the PI(s) (based on below-mentioned WHO criteria)³⁴, the CEC will determine the presence or absence of severe LRTI by reviewing all available clinical information related to respiratory disease, with a special focus on the following characteristics (“WHO” criteria)³⁴:

- Respiratory infection defined as cough or difficulty breathing

AND

- LRTI defined as fast breathing or peripheral capillary oxygen saturation (SpO_2) $<95\%$
AND
- ≥ 1 of the severe disease feature:
 - oximetry $<93\%$
 - lower chest wall indrawing

Determination of RSV Infection

A subject is considered RSV positive if the subject has a positive RT-PCR for RSV on nasal (mid-turbinate or nasopharyngeal) samples (central laboratory; see Section 9.2.2). If no central laboratory RT-PCR result is available, a positive test result (including commercial test results) for RSV from a local laboratory (if available) could be used to confirm RSV infection upon evaluation by the CEC.

If a test result for RSV is missing (ie, not available or not conclusive), the RTI will not be considered RSV-related.

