11.2. Sample Size Determination

The number of subjects chosen for this study will provide a preliminary safety and immunogenicity assessment. Control recipients (Nimenrix or placebo) are included for blinding and safety purposes and will provide additional control specimens for immunogenicity assays.

While mild to moderate vaccine reactions (local site and systemic responses) are expected, AEs that preclude further dose administration or more serious ones that would limit product development are not anticipated.

[Table 7](#) shows the probabilities of observing at least 1 AE at given true AE rates:

Table 7: Probability of Observing at Least One Adverse Event at a Given True Adverse Event Rate

True Adverse Event Rate	Probability of Observing at Least One Adverse Event in N Subjects	
	N=18	
0.5%	9%	
1%	17%	
2.5%	37%	
5%	60%	
10%	85%	
25%	99%	
50%	100%	

A monitoring rule for severe RSV-LRTI is described in Section 11.3.1.3. Based on this rule and assuming an event rate in controls of 1%, there is at least 80% power to halt enrollment in this or the next study if the incidence in the Ad26.RSV.preF group is approximately 25% or more.

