11.3.1.3. Monitoring Rule for Severe RSV-LRTI

In this section ‘severe RSV-LRTI’ refers to the assessment made by the CEC.

With respect to the secondary endpoint ‘severe RSV-LRTI’, a monitoring rule for severe RSV-LRTI is as follows.

- If 1 event (regardless of group) of ‘severe RSV-LRTI’ is observed, no analysis will be done. *Note:* However, the IDMC will be informed and may convene.
- As soon as 2 or more events (regardless of group) of ‘severe RSV-LRTI’ have been observed, confidence limits for the difference in proportions (using Wilson score method) between the Ad26.RSV.preF group and control group (pooling placebo/placebo/Nimenrix and placebo/placebo/placebo) will be constructed by the external statistician who is supporting the IDMC:
 - If the upper (one-sided) 95% confidence limit for the difference is $<10\%$: continue the study; if study enrollment is still ongoing, continue enrollment.
 - If the upper (one-sided) 95% confidence limit is $\geq 10\%$ and the lower (one-sided) 80% confidence limit is >0 : more frequent active monitoring of subjects, including weekly calls within the RSV season and more frequent medical review will be initiated.
 - If the upper (one-sided) 95% confidence limit is $\geq 10\%$ and the lower (one-sided) 95% confidence limit is >0 : halt enrollment in this study or the next study; more frequent active monitoring of subjects, including weekly calls within the RSV season and more frequent medical review for all enrolled subjects should be initiated.

For example: assuming complete enrollment, if 2 or 3 severe RSV-LRTI events are observed and all occurred in the Ad26.RSV.preF group, the lower (one-sided) 80% (but not the 95%)

confidence limit will be >0 and monitoring will be increased. If 4 severe RSV-LRTI events are observed and all occurred in the Ad26.RSV.preF group, the lower (one-sided) 95% confidence limit will be >0 and enrollment in all pediatric studies with Ad26.RSV.preF will be halted and monitoring of all enrolled subjects will be increased.

More details on this monitoring rule are specified in the IDMC charter.

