11.9. Data Review Committees

11.9.1. Clinical Endpoint Committee (CEC)

The CEC is an independent panel consisting of external medical experts with relevant experience in RSV in children. At all times during the study, the CEC will stay blinded, hence CEC members will not be part of the IDMC. Full details of CEC responsibilities, authorities, and procedures will be documented in its charter.

The CEC will assess suspected cases of severe LRTI and the occurrence of RSV infection. If the RTI is assessed to be a severe RSV-LRTI by the CEC (see Section 11.3.1.2), this will be shared with the IDMC which then might convene to run the monitoring rule.

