### 5.2. Analysis of RSV infection

The number and percentage of subjects with RTI and RSV confirmed RTIs will be tabulated.

As soon as 3 or more events (regardless of group) of 'severe RSV-LRTI' have been observed, the proportions per group and the confidence limits for the difference in proportions (using Wilson score method) between the Ad26.RSV.preF group and control group (pooling placebo/placebo/Nimenrix and placebo/placebo/placebo) will be constructed. The upper (one-sided) 95% confidence limit for the difference, the lower (one-sided) 95% confidence limit for the difference and the lower (one-sided) 80% confidence limit will be constructed.

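### The severe RSV-LRTI monitoring rule starts at 2 events in the Protocol but 3 in the SAP, and its worked example and power figure do not fit one method at 18 per arm

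*Protocol*

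**What the plan says.** Tallies are written Ad26.RSV.preF/control.

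- **Trigger.** Protocol 11.3.1.3 and the Synopsis construct one-sided Wilson limits for the difference in proportions once 2 or more severe RSV-LRTI events have occurred in either group. SAP 5.2 constructs them "As soon as 3 or more events (regardless of group) of" severe RSV-LRTI.
- **Levels.** If the upper 95% limit is at least 10%, a lower 80% limit above zero means increased monitoring, and a lower 95% limit above zero means halting enrolment in this or the next study (11.3.1.3).
- **Sample size.** Protocol 3.1 plans 36 subjects, 18 per group, and notes 37 enrolled at Amendment 6. SAP 1.2 plans 48, 24 per group.
- **Example.** For complete enrolment, 11.3.1.3 states: "if 2 or 3 severe RSV-LRTI events are observed and all occurred in the Ad26.RSV.preF group, the lower (one-sided) 80% (but not the 95"%) limit exceeds zero. Four events, all in the vaccine group, are said to cross the 95% limit.
- **Power.** With 1% in controls and about 25% in the vaccine group, 11.2 says "there is at least 80% power to halt enrollment in this or the next study".
- **Missing RSV results.** Protocol 11.3.1.2: "If a test result for RSV is missing (ie, not available or not conclusive), the RTI will not be considered RSV-related". Section 11.9.1 describes what goes forward: "If the RTI is assessed to be a severe RSV-LRTI by the CEC (see Section 11.3.1.2), this will be shared with the IDMC".

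**The concern.** This rule is the study's formal check for a preliminary sign of enhanced respiratory disease. The statistician supporting the IDMC has two texts with different starting points, and the gap between them contains a tally that the Protocol's own example places at the increased-monitoring level. The method is also underspecified. Neither document says whether the Wilson limits carry a continuity correction, and SAP 5.2 supports the method by citing a paper whose title announces a comparison of eleven methods. At 18 per arm that choice decides whether 3/0 is a monitoring result or a halt result.

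A lesser matter is that a severe LRTI confirmed by the CEC but lacking a conclusive RSV result is left out of the tally, and neither document plans to show what difference it would make.

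**Working it through.** **Inputs.** 18 per arm (3.1); rates 25% v 1% (11.2); one-sided 95% and 80% limits (11.3.1.3), so z = 1.645 and 0.842. The limits are Newcombe-Wilson: with d = p1 − p2 and single-arm Wilson limits (l, u), the lower limit is d − √[(p1 − l1)² + (u2 − p2)²].

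**The Protocol's power figure.** Sum the two binomial probabilities over all tallies at halt level. Uncorrected at 18/18, these are 3 or more against 0, 5 or more against 1, and rarer ones:

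- 0 control events: 0.8345 × 0.8647 = 0.7216
- 1 control event: 0.1517 × 0.4813 = 0.0730
- remainder: 0.0019
- total: 0.7965, or 79.7%

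Power reaches 80% at a vaccine-group rate of 25.2%, so the 11.2 statement reproduces with the uncorrected method.

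**The Protocol's example, same method.** For 3/0 at 18/18, p1 = 0.1667, l1 = 0.0686 and u2 = 0.1307. The lower 95% limit is 0.1667 − √(0.0980² + 0.1307²) = 0.1667 − 0.1634 = **+0.0033**. The upper limit is 0.352, so the halt condition is met, contrary to the example.

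**Continuity-corrected, 18/18.** 3/0 gives −0.0424 and 4/0 gives +0.0002, as in the example. But halting now needs 4 or more against 0, or 6 or more against 1: 0.8345 × 0.6943 + 0.1517 × 0.2825 + 0.0007 = 0.5794 + 0.0429 + 0.0007 = 0.623.

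| Arms, method | 3/0 lower 95% | 4/0 lower 95% | Power, 25% v 1% | Fits example | Fits 11.2 |
|---|---|---|---|---|---|
| 18/18 uncorrected | +0.0033 | +0.0460 | 79.7% | no | yes |
| 18/18 corrected | −0.0424 | +0.0002 | 62.3% | yes | no |
| 19/18 uncorrected | −0.0025 | +0.0382 | 69.8% | yes | no |
| 24/24 uncorrected | −0.0004 | +0.0314 | 84.8% | yes | yes |

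Of these, only the former 24/24 design satisfies both statements. The split of the 37 enrolled is not given; 19/18 is one possibility.

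**Trigger 2 against trigger 3, 18/18 uncorrected.** For 2/0, p1 = 0.1111; at 80%, l1 = 0.0629 and u2 = 0.0379. The lower 80% limit is 0.1111 − √(0.0482² + 0.0379²) = **+0.050**. The lower 95% limit is −0.039 and the upper 0.286, so this is the increased-monitoring level. The other two-event tallies (1/1, 0/2) do not reach it, so moving the trigger to 3 loses exactly the probability of 2/0: 0.0958 × 0.8345 = 0.080. The chance of at least increased monitoring falls from 94.2% to 86.2%. The chance of halting stays at 79.7%, because no two-event tally halts.

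**Untested cases (secondary), 18/18 uncorrected.** One untested vaccine-group case added to 2/0 moves the lower 95% limit from −0.039 to +0.003. One untested control case added to 3/0 moves it from +0.003 to −0.076. At 4/0, one more vaccine-group case changes no level.

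**The case against.** **On the trigger.** The SAP text matches the Protocol before Amendment 5 (trigger lowered from 3 to 2) and Amendment 6 (48 reduced to 36). SAP 1 names one planned IDMC analysis, at Day 8 in the first 12 toddlers, and allows further outputs on request. A reader might infer that the IDMC would remain unaware of two events. The documents do not support that: 11.3.1.3 says of a single event "However, the IDMC will be informed and may convene", and it leaves further detail to the IDMC charter, which was not available. What stands is that the two texts at hand give different instructions. A reader might also infer that the SAP trigger costs power to halt; it costs none.

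**On the example and power.** The limits govern and the example only illustrates. Nor is 79.7% against at least 80% at approximately 25% an error. Both points are fair, and the power statement taken alone is sound under the uncorrected method. They do not remove the conflict, because the method that supports the power figure contradicts the example.

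**On untested cases.** Here the objection is strong. The handling was a deliberate Amendment 4 choice. Same-day shipment, repeat swabs on worsening and local tests (9.2.2, 11.3.1.1), and caregiver swabs (Attachment 3), keep the group small. Only RSV-positive RTIs leave the (S)AE analyses, so an untested serious case stays in the SAE tables, and SAP 5.2 adds: "The number and percentage of subjects with RTI and RSV confirmed RTIs will be tabulated". The IDMC reviews unblinded data and convenes on any safety question (11.9.2). The data presentation specifications and both charters may already contain such a run; of the CEC, 11.9.1 says "Full details of CEC responsibilities, authorities, and procedures will be documented in its charter". A reader might infer that enhanced-disease cases are hidden or that the rule loses a known amount of power. Neither follows: the documents give no rate of missing results, and 11.9.1 does not forbid passing these cases on. What remains is that their effect on the rule appears only if someone asks, while Attachment 3 foresees that a sample might not be taken.

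**Conclusion.** The rule is wrong as written in two respects.

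1. Protocol and SAP differ on the trigger (2 v 3) and the planned sample size (36 v 48). At 18/18 and 25% v 1%, the trigger difference is worth 8.0 percentage points in the chance of reaching at least increased monitoring, and nothing in the chance of halting.
2. At 18/18 neither the uncorrected nor the continuity-corrected Wilson method satisfies both the 11.3.1.3 example and the 11.2 power statement. The pattern suggests figures carried over from 24 per arm, but that is an inference.

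These results assume independent binomial counts, the 11.2 rates, and Newcombe-Wilson limits. With 37 enrolled against a target of 36, the practical effect is mainly on the monitoring level and the next study.

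The untested-case point is secondary: for consideration only, with low confidence. It matters only if such a case occurs and the confirmed tally is then at a boundary.

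**What to change.** 1. Reconcile the SAP 5.2 trigger and the SAP 1.2 sample size with the current Protocol.
2. State in 11.3.1.3 and SAP 5.2 whether the Wilson limits use a continuity correction. Then recompute and restate the worked example and the 11.2 power figure with that method at the current sample size, using the actual split if it is not 18/18.
3. Optional: keep the confirmed definition for the endpoint and the governing rule. Add a non-governing table for the IDMC with the same limits, counting CEC-confirmed severe LRTIs with a missing or inconclusive RSV result, run once confirmed plus untested events reach the trigger. Say in 11.9.1 that the CEC passes these cases on. If a charter or the data presentation specifications already provides this, a citation is enough.

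Items 1 and 2 need a few sentences and a short recalculation. Item 3 needs one or two sentences and one small table. Its price is specificity: assuming no vaccine effect, 1% severe RSV-LRTI in both arms, and untested non-RSV cases adding 1, 2 or 3% in both arms, the supportive table would show at least the increased-monitoring level in 3.6, 6.3 or 9.0% of trials, against 1.2% for the confirmed count (18/18, uncorrected). That is why it should not govern.

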11.3.1.3. Monitoring Rule for Severe RSV-LRTI

In this section ‘severe RSV-LRTI’ refers to the assessment made by the CEC.

With respect to the secondary endpoint ‘severe RSV-LRTI’, a monitoring rule for severe RSV-LRTI is as follows.

- If 1 event (regardless of group) of ‘severe RSV-LRTI’ is observed, no analysis will be done. *Note:* However, the IDMC will be informed and may convene.
- As soon as 2 or more events (regardless of group) of ‘severe RSV-LRTI’ have been observed, confidence limits for the difference in proportions (using Wilson score method) between the Ad26.RSV.preF group and control group (pooling placebo/placebo/Nimenrix and placebo/placebo/placebo) will be constructed by the external statistician who is supporting the IDMC:
 - If the upper (one-sided) 95% confidence limit for the difference is $<10\%$: continue the study; if study enrollment is still ongoing, continue enrollment.
 - If the upper (one-sided) 95% confidence limit is $\geq 10\%$ and the lower (one-sided) 80% confidence limit is >0 : more frequent active monitoring of subjects, including weekly calls within the RSV season and more frequent medical review will be initiated.
 - If the upper (one-sided) 95% confidence limit is $\geq 10\%$ and the lower (one-sided) 95% confidence limit is >0 : halt enrollment in this study or the next study; more frequent active monitoring of subjects, including weekly calls within the RSV season and more frequent medical review for all enrolled subjects should be initiated.

For example: assuming complete enrollment, if 2 or 3 severe RSV-LRTI events are observed and all occurred in the Ad26.RSV.preF group, the lower (one-sided) 80% (but not the 95%)

confidence limit will be >0 and monitoring will be increased. If 4 severe RSV-LRTI events are observed and all occurred in the Ad26.RSV.preF group, the lower (one-sided) 95% confidence limit will be >0 and enrollment in all pediatric studies with Ad26.RSV.preF will be halted and monitoring of all enrolled subjects will be increased.

More details on this monitoring rule are specified in the IDMC charter.

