3. STUDY DESIGN AND RATIONALE

3.1. Overview of Study Design

This is a multi-center, randomized, observer-blindⁱ, Phase 1/2a study, to be conducted in 36 male and female RSV-seronegative toddlers aged ≥ 12 to ≤ 24 months.

Each subject's RSV serostatus will be assessed by RSV enzyme immunoassay (EIA) at screening^j (see Section 9.1.3.1). *Note*: serostatus may be assessed via this assay if available from a different study of the sponsor (VAC18194RSV2001). If done within 42 days of first dose, this assessment would not have to be repeated in the absence of a history of respiratory infection during that period. Additionally, the seronegative status will be confirmed by the absence of an anamnestic humoral immune response (which is usually observed 7-10 days post antigen re-exposure in RSV seropositive subjects) from blood samples taken 7 days after the first dose.

ⁱ *Note*: The vaccine administrator will be unblinded but will have no other study function following dosing. The site staff or qualified professional staff who will do the observation and the subjects will be blinded.

^j The cut-off for seronegativity is a titer < 1 EIA unit.

Subjects will be randomized 1:1 to receive either Ad26/Ad26/Ad26 (at 2.5×10^{10} vp) or placebo/placebo/Nimenrix ^{k,1} (or placebo/placebo/placebo) (Table 4).

Table 4: Study Design VAC18194RSV2002

Group	N ^a	Day 1	Day 29/Week 4	Day 57/Week 8
RSV-seronegative toddlers 12 to 24 months				
Group 1	18	Ad26.RSV.preF (2.5×10^{10} vp)	Ad26.RSV.preF (2.5×10^{10} vp)	Ad26.RSV.preF (2.5×10^{10} vp)
Group 2	18	Placebo (saline)	Placebo (saline)	Nimenrix ^b or Placebo (saline)

N = number of subjects; vp = viral particles

^a: At the time of Amendment 6, 37 subjects have been enrolled.

^b: In countries where the commercial vaccine Nimenrix is licensed, placebo (0.9% saline) can be replaced with Nimenrix as the Day 57 vaccination for the study subjects in the control group, in accordance with the local label and local regulations, and unless contra-indicated. Nimenrix will be administered, only if permitted by the subject's parent/legal guardian and following PI assessment on a case-by-case basis as vaccination with Nimenrix outside this study might be preferred (joint parent/legal guardian and PI decision). In the US, Nimenrix will not be used unless it has been licensed for use or an Investigational New Drug (IND) has been submitted.

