5. STUDY VACCINE ALLOCATION AND BLINDING

Study Vaccine Allocation

Central randomization will be implemented in this study. Subjects will be randomly assigned to a treatment group based on a computer-generated randomization schedule prepared before the study by or under the supervision of the sponsor. The randomization will be balanced by using randomly permuted blocks. No stratification will be applied.

The randomization ratio is 1:1.

The interactive web response system (IWRS) will assign a unique code, which will dictate the group assignment for the subject. The requestor must use his or her own user identification and personal identification number when contacting the IWRS, and will then give the relevant subject details to uniquely identify the subject.

If randomized subjects are withdrawn from vaccination before the first dose is administered, additional subjects may be recruited to replace these subjects at the discretion of the sponsor. Any replacement subject will be assigned to the same group as the original (discontinued) subject. The replacement subject's randomization number will equal the randomization number of the discontinued subject +1000 (for example subject 0001 would be replaced by subject 1001). These additional subjects should also be randomized through IWRS.

Any randomized subject who is withdrawn from the study for reasons other than due to an AE after the first dose but before the second dose might be replaced at the discretion of the sponsor. Any replacement subject will be assigned to the same group as the original (discontinued) subject. The replacement subject's randomization number will equal the randomization number of the discontinued subject +2000.

Every effort will be made to determine the serostatus of subjects. During the study, any subject who was assessed as seronegative at screening and who subsequently shows an anamnestic response at Day 8 will be replaced if possible.

Blinding

The investigator will not be provided with randomization codes until the final analysis is performed. The codes will be maintained within the IWRS, which has the functionality to allow the investigator to break the blind for an individual subject.

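### The severe RSV-LRTI monitoring rule is not exhaustive: balanced and near-balanced event splits at 18 per group meet none of its three conditions

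*Protocol*

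**What the plan says.** Protocol 11.3.1.3, repeated in the synopsis, sets the rule. With one event the limits are not computed: if one event "is observed, no analysis will be done", although the IDMC is informed and may convene. "As soon as 2 or more events (regardless of group) of ‘severe RSV-LRTI’ have been observed", the external statistician computes Wilson score limits for the difference in proportions, Ad26.RSV.preF minus pooled control. Three actions follow:

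- **Continue**: upper one-sided 95% limit below 10%. The instruction is "continue the study; if study enrollment is still ongoing, continue enrollment".
- **Increased monitoring**: upper limit at least 10% and lower one-sided 80% limit above 0.
- **Halt enrollment**, with increased monitoring: upper limit at least 10% and lower one-sided 95% limit above 0.

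Section 11.3.1.3 refers further detail to the IDMC charter, which is not among the documents. SAP 5.2 lists the same three limits, still with a trigger of three events, and gives no actions.

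On size, Protocol 3.1 describes a study "to be conducted in 36 male and female RSV-seronegative toddlers", and Section 5 states "The randomization ratio is 1:1", hence 18 per group. The footnote to the design table adds: "At the time of Amendment 6, 37 subjects have been enrolled".

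**The concern.** The three conditions do not cover every result. If the upper limit is at least 10% and the lower 80% limit is 0 or less, the continue condition fails and so do both escalation conditions. With 18 per group the interval is wide, so this is where results with similar event counts in the two groups fall.

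The rule is the protocol's formal safeguard against enhanced respiratory disease, and Protocol 11.10 ties a study pause to its criteria. A decision rule of this kind should give an answer for every result that triggers it, and above all for the results expected when the vaccine does no harm. If it is silent there, the protocol itself does not say what follows, and the choice is made after unblinded data have been seen unless the charter settles it.

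**Working it through.** **Inputs.** 18 per group (Protocol 3.1 and 5); trigger of two or more events in total, and the three tiers (11.3.1.3); control rate of 1% and vaccine rate of about 25% for the power statement (11.2). All other event rates below are assumptions, shown as a range.

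**Interval.** For x events in n subjects, with p = x/n, the Wilson limits are

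l, u = [2np + z² ∓ z√(z² + 4np(1 − p))] / [2(n + z²)].

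For vaccine (1) minus control (2), the hybrid score limits are

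upper = p₁ − p₂ + √[(u₁ − p₁)² + (p₂ − l₂)²]

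lower = p₁ − p₂ − √[(p₁ − l₁)² + (u₂ − p₂)²]

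with z = 1.645 for one-sided 95% and 0.842 for one-sided 80%.

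**Reproducing the plan's figure.** Protocol 11.2 states at least 80% power to halt at about 25% against 1%. Summing the binomial probabilities of all halt outcomes at 18/18 gives 79.6% (81.9% at 26%). With a continuity correction it is 62.3%. The uncorrected interval comes close to the stated power and is the base case.

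**Two splits by hand at 18/18** (vaccine-control).

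- 1-1: p = 0.0556 in both groups; 95% Wilson limits 0.0125 and 0.2148. Upper = √(0.1592² + 0.0431²) = 0.165. The 80% Wilson limits are 0.0247 and 0.1200, so lower 80% = −√(0.0309² + 0.0644²) = −0.071. No tier.
- 1-2: p₂ = 0.1111, l₂ = 0.0375. Upper = −0.0556 + √(0.1592² + 0.0736²) = 0.120. No tier.

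**All splits with 2 to 6 events at 18/18.**

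| Tier | Splits, with upper 95% limit where useful |
|---|---|
| None | 1-1 (16.5%), 2-1 (23.6%), 1-2 (12.0%), 2-2 (19.0%), 3-2 (25.5%), 2-3 (14.5%), 3-3 (20.9%), 2-4 (just over 10.0%) |
| Continue | 0-2 (3.9%), 0-3 (−0.3%), 1-3 (7.6%), 0-4, 1-4 (3.2%), 0-5, 1-5, 0-6 |
| Increased monitoring | 2-0, 3-1, 4-1, 4-2 |
| Halt | 3-0, 4-0, 5-0, 6-0, 5-1 |

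Eight of 25 splits (32%) have no tier. Continue is reached only when controls have at least two more events than vaccinees, and 2-4 shows that even this is not always enough.

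**By probability.** Sum the binomial probabilities of the no-tier splits and divide by P(at least 2 events). At 1% in both groups, P(at least 2) = 1 − 0.99³⁶ − 36 × 0.01 × 0.99³⁵ = 1 − 0.6964 − 0.2532 = 0.050. The no-tier probability is 0.027, so the share is 54%.

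| Vaccine / control risk | No tier, share of triggered analyses |
|---|---|
| 1% / 1% | 54% |
| 2.5% / 2.5% | 57% |
| 5% / 5% | 58% |
| 10% / 10% | 59% |
| 5% / 1% | 31% |
| 10% / 1% | 16% |
| 25% / 1% | 2.5% |

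Under equal risk, 19% to 23% of triggered analyses reach continue.

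**Effect of the cut from 24 to 18.** At 24/24, 1-1, 2-1 and 2-2 already had no tier. The split 1-2 had an upper limit of −0.0417 + √(0.1251² + 0.0553²) = 0.095 and fell in continue; at 18/18 it is 12.0%. The no-tier share rises from 49% to 54% at 1%/1%, and from 46% to 58% at 5%/5%.

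**Sensitivity.** With continuity correction, 11 of the 25 splits have no tier. With 37 subjects (19/18 or 18/19) the no-tier splits up to five events are unchanged.

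**Boundaries.** Over all triggered splits at 18/18, none has an upper limit below 10% together with a lower 80% limit above 0.

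**The case against.** The strongest reply is that the rule lists what triggers escalation: where neither escalation condition is met, nothing is prescribed and the study goes on. The synopsis has the IDMC review unblinded data and make a recommendation, so the committee has a role at 1-1, and its charter may fill the gap. Further, 37 subjects were already enrolled against a target of 36, so little enrollment was left to continue or halt, and at a 1% risk the rule rarely triggers.

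Much of this stands. A reader might infer that the study may not continue at 1-1, or that the IDMC would have to improvise. The documents support neither: nothing orders a stop, and the charter cannot be seen.

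It does not remove the defect. If failing both escalation conditions already meant continue, the 10% upper-limit test would do no work at 18/18, because no outcome meets it while also having a lower 80% limit above 0. The protocol nevertheless makes that test the stated condition for continuing. Nor is the rule idle once enrollment is complete: follow-up runs through two RSV seasons, one tier changes monitoring, and the halt tier reaches the next study. An unseen charter cannot be assumed to repair the protocol's text.

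**Conclusion.** The point holds as a gap in the wording, and the gap itself needs no assumption about event rates. Which splits fall into it depends on 18 per group and on the uncorrected interval; how often depends on assumed risks. It is most frequent when the groups have equal risk (54% to 59% of triggered analyses, though only about 2.7% of trials at 1%/1%) and fades as the vaccine risk rises (2.5% of triggered analyses at 25% against 1%).

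Three stronger readings are tempting and should not be drawn:

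- *Most triggered outcomes have no tier.* This is true only as a probability under equal risk; by count it is about a third.
- *The cause is that 0-0 already gives an upper limit of 13.1%.* That limit shows how wide the interval is at 18 per group, but 0-0 never triggers the rule. The cause is the missing branch.
- *Amendment 6 created the gap.* It was present at 24 per group; the smaller groups widened it.

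This should be corrected, but it does not undermine the escalation tiers themselves.

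**What to change.** Reconcile the tiers in 11.3.1.3 and the synopsis, consistently with the IDMC charter, so that every triggered outcome falls in exactly one. State explicitly what applies when the upper 95% limit is at least 10% and the lower 80% limit is 0 or less. Which action that is, and whether the 10% test is kept, is for the sponsor and the IDMC to decide. Since no outcome at 18/18 combines an upper limit below 10% with a lower 80% limit above 0, closing the gap need not move the increased-monitoring or halt boundary.

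While the text is open, name the interval variant and reconcile the worked example with the rule: at 18/18 the uncorrected lower 95% limit for 3-0 is +0.3%, which meets the halt condition, whereas the example says three events do not.

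The cost is wording in 11.3.1.3, the synopsis and, if needed, the charter, issued through a protocol amendment. It needs no new data and no change in sample size.
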